3.1 Assessment and management of risk

The table below summarises the risks, frequencies and mitigations of the IMP(s)

Name of IMP(s) / NIMP	Potential risk	Risk Frequency	Risk Management
Exenatide	Weight loss	Common	Underweight people will not be recruited. Patients losing weight too rapidly (>10% body weight per month) will temporarily stop the IMP.
Exenatide	Nausea/ Vomiting	Very common	In most cases, nausea is mild and self limiting. In more severe cases, patients will be prescribed a temporary course of Domperidone.
Exenatide	Diarrhoea	Very common	In most cases, diarrhoea is mild and self limiting. Symptomatic and supportive treatment will be given as necessary.
Exenatide	Decreased Appetite	Common	In most cases, loss of appetite is transient and self limiting. Weight will be measured and exenatide will be transiently stopped if weight loss exceeds 10% of body weight per month.
Exenatide	Headache	Common	In most cases, headache is transient and self limiting. Participants will be assessed and given standard of care treatment for persistent headaches.
Exenatide	Dizziness	Common	In most cases, dizziness, is transient and self limiting. Participants will be assessed and given standard of care treatment for persistent dizziness.

Short title: Exenatide once-weekly as a treatment for Multiple System Atrophy Sponsor code: 125591

Exenatide	Dyspepsia/ Abdominal pain	Common	In most cases, abdominal pain is transient and self limiting. Any suspicion of pancreatitis will lead to temporary discontinuation of exenatide until pancreatitis has been excluded. Participants will be assessed and given standard of care treatment for persistent abdominal pain.
Exenatide	Abdominal Distension/ Flatulence	Common	In most cases, abdominal distension/flatulence is transient and self limiting. Participants will be assessed and given standard of care treatment for persistent abdominal distension/flatulence.
Exenatide	Constipation	Common	In most cases, constipation is transient and self limiting. Participants will be assessed and given standard of care treatment for persistent constipation.
Exenatide	Anaphylactic reaction	Rare	Patients will self administer their first Exenatide injection in the trial centre under supervision by the trial team.

The table below summarise the risks and mitigations of all test above standard care that are being performed in a table:

Intervention	Potential risk	Risk Management

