6.3 Storage and handling of IMP(s) at site

All IMP aspects of the trial at participating sites are the responsibility of the PI, who may delegate this duty to the local pharmacist or other appropriately trained personnel. The delegation of duties must be recorded on the Staff Signature and Delegation of Tasks.

Storage and handling (e.g., labelling) of the IMP will be completed in accordance with the relevant SPC and summary of drug arrangements. Exenatide requires refrigerated storage (2-8°C). Once removed from the refrigerator, Exenatide needs to stand at room temperature for at least 15 minutes before administration. All patients will be instructed how to operate the pen device and to perform the injections. They will perform their first injection with supervision of the trial team at the end of the baseline visit.

For home visits, dispensing of IMP will be performed by trial pharmacy and transported to the patient in an appropriate cool bag with temperature logger by the clinical trial team. The trial team member will check the temperature logger to ensure the temperature has stayed within the range 2-8°C. If the temperature has fallen out of range the IMP must not be dispensed to the patient and should be returned to the trial pharmacy.

Detailed instructions are contained in the summary of drug arrangements.

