Patients developing clinical suspicion of thyroid malignancy will receive treatment according to NHS standard of care and the trial medication will be stopped.

Patients experiencing excessive/undesirable weight loss (>10% of body weight during a 12 week interval) or unacceptable adverse effects will have a clinical assessment and a decision regarding temporary withdrawal of study medication will be made.

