8.4 Subsequent assessments and procedures

Week 4 (+/-1 week) – telephone call

The study nurse will call the participants to ensure the participants are taking their medication according to the protocol requirements and completing their trial diary as required. They will also perform a concomitant medication and AE check.

Week 12 assessments – Visit 3

At 12 weeks after baseline evaluation, each patient will be telephoned 1 week prior to remind them of their visit

Participants will attend the research centre for the following trial procedures:

- Physical Examination (if deemed necessary by trial clinician for clinical purposes)
- Routine blood tests (FBC, U&E, LFT, glucose, amylase, HbA1c, PT and APTT)
- Serum collection
- Vital signs including weight
- UMSARS Part II (videotaped)
- UMSARS Part I, III and IV
- The Unified Dystonia Rating Scale
- MoCA
- Timed Motor tests
- BDI-II
- Concomitant Medications review
- Adverse Events review
- Dispensing of 12 exenatide (Bydureon or Bydureon BCise) pens (if randomised to receive exenatide).

All participants will be invited for face to face visits at all timepoints. If a participant is unable or unwilling to attend any of the follow up assessments (12,24,36,48,96 weeks), they may be offered the option of a home visit by one or more members of the trial clinical team if staffing levels permit. These participants will be asked to consent to home visits. Assessments will be performed as per protocol. Weight will be measured only if the participant is able to stand, and weighing scales are available. Dispensing of IMP will be performed by trial pharmacy and transported to the patient in an appropriate Cool Bag with temperature logger by the clinical trial team.

Week 24 assessments – Visit 4

At 24 weeks after baseline evaluation, each patient will be telephoned 1 week prior to remind them of their visit. They will be asked not to have eaten and to have drunk water only for 6 hours to enable fasting blood samples to be taken.

Participants will attend the research centre for the following trial procedures:

- Physical Examination (if deemed necessary by trial clinician for clinical purposes)
- Neurological Examination (if deemed necessary by trial clinician for clinical purposes)
- Fasting blood tests (FBC, U&E, LFT, glucose, amylase, insulin, c-peptide, HbA1c)
- Serum collection
- Vital signs including weight
- UMSARS Part II (videotaped)

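### Section 8.4 lets weighing be skipped at home visits while pens are still delivered, so the protocol's own weight-loss rule cannot be applied for that interval

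*Protocol*

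**What the plan says.** **Home visits (Protocol 8.4).** The option opens with "If a participant is unable or unwilling to attend any of the follow up assessments (12,24,36,48,96 weeks" and depends on staffing. The general rule is "Assessments will be performed as per protocol". The next sentence makes an exception: "Weight will be measured only if the participant is able to stand, and weighing scales are available". The one after that deals with supply: "Dispensing of IMP will be performed by trial pharmacy and transported to the patient in an appropriate Cool Bag with temperature logger".

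**Supply (Protocol 8.4 and 6.3).** In the exenatide arm 12 pens are due at each of weeks 12, 24 and 36; the week 12 list reads "Dispensing of 12 exenatide (Bydureon or Bydureon BCise) pens (if randomised to receive exenatide". Section 6.3 adds a bar for home supply: "If the temperature has fallen out of range the IMP must not be dispensed to the patient". Neither section mentions weight in connection with home supply.

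**Weight as a safeguard.** In the risk table of Protocol 3.1, the "Decreased Appetite" row says that weight is measured and links a temporary stop of exenatide to a rate of weight loss. It gives no exception for home visits. Section 8.3.1 begins "Patients experiencing excessive/undesirable weight loss (>10% of body weight during a 12 week interval" and leads to a clinical assessment and a decision on temporary withdrawal. Section 8.4 lists weight with the vital signs at every follow-up visit. Appendix 1 has a weight row, and its notes do not mention the home-visit exception.

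**The concern.** Weight loss is a listed risk of exenatide, and the protocol manages it through a measured change in body weight. Section 8.4 removes the measurement at some home visits and leaves the supply of drug in place. It offers no substitute measure and does not say how a missed weight is to be recorded.

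Two comparisons within the protocol suggest an oversight. A lumbar puncture missed because the week 48 visit is at home must be logged as a protocol deviation, whereas a missed weight, which feeds a treatment decision, has no such rule. The COVID-19 plan in Appendix 2 requires a telephone check before drug is couriered, and weight is among the topics to be asked about. The home-visit text, where staff are in the room, has no equivalent.

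At stake is whether a safeguard that the protocol relies on operates at those visits.

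**Working it through.** The plan gives no figure of its own here, so there is none to reproduce. The check sets the texts side by side and then counts doses and weeks.

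**1. Can 8.4 and 3.1 both hold?** Section 3.1 states the measurement as a fact, without condition. Section 8.4 requires two conditions together: the participant can stand, and scales are there. If either fails, no weight is taken. The two texts disagree for that visit.

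**2. Can 8.3.1 be applied?** Its criterion is a change over 12 weeks, so it needs a weight at both ends. Scheduled on-treatment weights fall at weeks 0, 12, 24, 36 and 48, which gives four such intervals. A missing weight at week 12, 24 or 36 is the end of one interval and the start of the next, so two of the four cannot be assessed.

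**3. Does supply depend on weight?** In the home-supply text of 8.4 and 6.3 it does not. The only condition stated there is temperature.

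**4. Size.** Inputs:
- treatment length: 48 weekly doses (8.3);
- pens due at each of weeks 12, 24 and 36: 12 (8.4);
- spacing of weights: 12 weeks (8.4).

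For k consecutive unweighed dispensing visits:
- doses supplied without a current weight = 12 × k;
- share of treatment = 12 × k / 48;
- gap between weights = 12 × (k + 1) weeks.

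| k | Doses | Share of 48 | Gap between weights |
|---|---|---|---|
| 1 | 12 | 25% | 24 weeks |
| 2 | 24 | 50% | 36 weeks |
| 3 | 36 | 75% | 48 weeks |

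The k = 3 row runs from baseline and assumes that a weight is taken at week 48. Weeks 48 and 96 involve no dispensing, so the point concerns weeks 12, 24 and 36. The documents do not say how many home visits are expected. The first row is therefore the effect of a single event, and the other rows show the range that the text allows.

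**5. Who is affected?** Entry requires the ability to walk 10 metres (7.2), so inability to stand would have to arise during follow-up. The scales condition can affect anyone visited at home, including those who simply prefer not to travel.

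**The case against.** The strongest reply is that 8.4 is a sensible accommodation whose alternative may be no visit at all. Trial clinical staff see the participant in person. Adverse-event review and blood tests continue, and so does examination where the clinician thinks it necessary. Sections 8.8 and 8.10 allow treatment to be stopped for any change in condition that warrants it, and 8.3.1 itself also covers unacceptable adverse effects. All of this stands. Clinical oversight continues at a home visit; what is lost is the measured criterion. The summary of drug arrangements, which 6.3 cites and which is not among the documents, may also contain a further check.

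Four stronger readings are tempting and are not supported:

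- **That participants continue with no weight on record.** Weight is taken at screening, and baseline vital signs include it by the definition in 8.6. What may be missing is a current weight.
- **That the gap falls only on the most disabled.** This fits the standing condition but not the scales condition.
- **That large losses would go unseen.** Compounding successive losses of 10% gives striking totals, but the documents give no rate of weight loss. Losses of exactly 10% would not meet the 8.3.1 criterion, which is more than 10%, even if every weight were taken.
- **That comparisons of weight change by arm would be biased in favour of exenatide.** The SAP lists weight as a baseline characteristic (6.2) and a collected measure (Table 1) but plans no analysis of weight change. The waiver applies to both arms, and nothing shows that unweighed participants lose more weight.

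**Conclusion.** The point holds as a gap in safety monitoring, modest in size and cheap to close. Section 8.4 contradicts 3.1, and where it is used 8.3.1 cannot be applied for the interval ending at that visit or for the one that follows. One unweighed dispensing visit means 12 of 48 doses (25%) supplied without a current weight, and 24 weeks between weights.

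This assumes that the full 12 pens are delivered, that the neighbouring scheduled weights are taken, and that no document outside the protocol and SAP adds a check. Unweighed continuation is permitted by the text, not certain, and its frequency cannot be estimated from the documents. It does not affect the primary analysis.

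**What to change.** 1. Reconcile 8.4 with 3.1, 8.3.1 and Appendix 1, so that they agree on when weight is measured and what happens when it is not. In doing so, note that 3.1 works with a monthly rate and a stop, while 8.3.1 works with a 12-week interval and a decision. Scheduled weights are 12 weeks apart, so a monthly rate is not observed directly even when every weight is taken. The sponsor's clinicians must settle which wording applies.
2. Make portable scales standard home-visit equipment and delete their availability as a condition in 8.4. The team already carries a cool bag and temperature logger.
3. Record each weight not obtained, with the reason (for example, the participant cannot stand), as a CRF item that the investigator reviews. The deviation log for a missed lumbar puncture is the model.

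The cost is a scale, one CRF item and a wording change, with no added visit, staff or procedure. A standing scale does not help participants who cannot stand; for them the gain is that the gap is recorded and reviewed. Any clinical action on a missed weight, or on dispensing, is for the sponsor's clinicians.

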8.7 Assessment of IMP/NIMP compliance

The importance of compliance with the trial protocol will be explained to the participant at baseline and at each follow up visit. Compliance will be optimised by informing all participants of the most commonly experienced side effects and ways of minimising these. Participants will be given adequate instruction regarding administration of injections and will be provided with a diary to record administration of IMP throughout the trial.

Compliance will be assessed by directly questioning patients at each visit, and if applicable carers will also be asked to provide estimates of compliance, along with review of the drug administration diary. Reasons for non-compliance will be sought and addressed as far as possible at each follow up visit.

Biological samples will be collected from each participant at each visit. These will include serum samples to allow measurement of Exenatide levels if indicated. Participants will be aware that their compliance will be measurable on the basis of these results. All analyses will be performed at the end of the trial. Guidance for sample collection and transport can be found in the Laboratory Manual.

8.8 Discontinuation/withdrawal of participants

In consenting to participate in the trial, participants are consenting to trial treatment, assessments, follow-up and data collection.

Discontinuation of Trial Treatment for clinical reasons

A participant may be withdrawn from trial treatment whenever continued participation is no longer in the participant's best interests, but the reasons for doing so must be recorded. Reasons for discontinuing treatment may include

- disease progression whilst on therapy
- unacceptable toxicity
- intercurrent illness which prevents further treatment
- patients withdrawing consent to further trial treatment

Any alterations in the participant's condition which justifies the discontinuation of treatment in the site investigator's opinion

- Persistent non-compliance to protocol requirements

The decision to withdraw a participant from treatment must be recorded in the CRF and medical notes and the sponsor when required should be notified in writing.

In these cases participants remain within the trial for the purposes of follow-up for safety and or data analysis according to the treatment option to which they have been allocated.

Participant withdrawal from trial treatment

If a participant expresses their wish to withdraw from trial treatment, sites should explain the importance of remaining on trial follow-up and seek permission to allow use of routine follow-up data to be used for trial purposes. The importance of safety follow-up should be emphasised to the participant in the Participant Information Sheet.

Short title: Exenatide once-weekly as a treatment for Multiple System Atrophy Sponsor code: 125591

The decision of the participant to withdraw from treatment must be recorded in the participant's CRF and medical notes in the electronic health record system, EPIC.

The participant may withhold their reason for withdrawal however, if the participant gives a reason for their withdrawal, this should be recorded.

Withdrawal of Consent to Data Collection

If a participant explicitly states they do not wish to contribute further data to the trial their decision must be respected and recorded in the participant's notes in the electronic health record system, EPIC.

Loss to follow-up

If a participant is lost to follow-up at a site every effort should be made to contact the participant's GP to obtain information on the participant's status

8.9 Replacements

Participants who withdraw from the trial prior to Week 12 (visit 3) will be replaced and their replacement randomised to maintain adequate numbers of participants reaching the 12 week assessment.

8.10 Stopping rules

The trial may be stopped before completion for the following reasons:

- On the recommendation of the TSC or DMC
- On the recommendation of the sponsor and CI

Individual participant stopping rules include:

- Unacceptable treatment toxicity or adverse event.
- Inter-current illness that prevents further treatment
- Any change in the participant's condition that in the clinician's opinion Justifies the discontinuation of treatment

If a stopping rule is reached safety data will be reviewed and a decision on continuation will be made by the TMG with input from the sponsor.

8.11 Definition of End of Trial

The expected duration of the trial is 4 years from recruitment of the first participant. The end of the trial is the date of the last follow up of the last participant.

9 Recording and reporting of adverse events and reactions

Collection, recording and reporting of adverse events (including serious and non-serious events and reactions) to the sponsor will be completed according to the sponsor's SOP (INV/S05).

9.1 Definitions

Term	Definition
Adverse Event (AE)	Any untoward medical occurrence in a patient or clinical trial participant administered a medicinal product and which does not necessarily have a causal relationship with this treatment. Therefore an AE can be any unfavourable or unintended change in the structure (signs), function (symptoms) or chemistry (laboratory data) in a participant to whom an IMP or procedural intervention has been administered, including occurrences which are not necessarily caused by or related to that product.
Adverse Reaction (AR)	Any untoward and unintended response in a participant to an investigational medicinal product which is related to any dose administered to that participant. This includes medication errors, uses outside of protocol (including misuse and abuse of product)
Serious Adverse Event (SAE), Serious Adverse Reaction (SAR) or Unexpected Serious Adverse Reaction	Any adverse event, adverse reaction or unexpected adverse reaction, respectively, that: 
 • results in death, • is life-threatening*, • requires hospitalisation or prolongation of existing hospitalisation**, • results in persistent or significant disability or incapacity, or • consists of a congenital anomaly or birth defect
	Some medical events may jeopardise the subject or may require an intervention to prevent one of the above characteristics/consequences. Such important medical events should also be considered as serious.
	*A life-threatening event, this refers to an event in which the participant was at risk of death at the time of the event; it does not refer to an event which hypothetically might have caused death if it were more severe.
	** Hospitalisation is defined as an in-patient admission, regardless of length of stay. Hospitalisation for pre-existing conditions, including elective procedures do not constitute an SAE.
Suspected Unexpected Serious	A serious adverse reaction, the nature, severity or outcome of which is not consistent with the Reference Safety Information.

Adverse Reaction (SUSAR)	
Reference Safety Information (RSI)	A list of medical events that defines which reactions are expected for the IMP being administered to clinical trial subjects, and so do not require expedited reporting to the Competent Authority. It is contained in a specific section in the Summary of product characteristics (SmPC) or the Investigator Brochure (IB).

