- Concomitant Medication: All over-the-counter or prescription medication, vitamins, and/or herbal supplements will be recorded.

- The Montreal Cognitive Assessment is a 30-point test that assesses several cognitive domains to detect cognitive impairment.
- The Beck's Depression Inventory-II is a patient rated depression severity scale.
- The Unified MSA Rating Scale (UMSARS) is a multidimensional, reliable, and valid scale for semi quantitative assessment of MSA patients with high internal consistency and substantial-to-excellent interrater agreement and is sensitive to change. It focuses on all aspects of the disorder, including autonomic, cerebellar, and parkinsonism manifestations. USMARS has an Activities of Daily Living score (UMSARS Part 1, 12 questions); a Motor Examination score (UMSARS Part 2, 14 questions); Autonomic examination score (UMSARS Part 3) and a global disability scale (UMSARS Part 4). Part 2 will be videotaped to ensure there is the option to retrospectively score the participants by blinded raters if there are concerns regarding bias in view of this being an open label trial. All videos will be stored in an appropriate secure encrypted storage facility which can only be accessed by members of the research team.
- The Composite Autonomic Symptom (COMPASS) Select is a subset of the full COMPASS consisting of 46 questions in 5 domains (orthostatic intolerance, secretomotor, bladder, constipation, and sleep), leading to a total score between 0 and 125, with a higher score indicating greater impairment
- The COMPASS Change Scale is a derivation of COMPASS-select in which the participants score their change in autonomic symptoms since their last exam. It comprises 26 retrospective questions in which participants scored how much their autonomic symptoms had changed. It is divided into change of 6 autonomic function domains (or 5 in women) [i.e. orthostatic intolerance, sexual failure (erectile dysfunction, male only), bladder disorder, secretomotor disorder, constipation and sleep disorder] with a maximum score of 160 for men and 150 for women (Wenning GK et al., 2007).
- MSA-QoL scale is a validated 40 item self-completed questionnaire in which a participant is asked to record the problems due to their MSA over the preceding 4 weeks.
- Timed Motor Tests include a hand tapping task to evaluate the number of hand taps that an individual can perform within 30 seconds and a timed, sit, stand, walk task.

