Unexpected	An adverse event which is not consistent with the information about the IMP listed in current approved Reference Safety Information (RSI) for the trial.

The RSI to be used to assess expectedness against the IMP is:

SmPC for Bydureon (exenatide) 2 mg for prolonged-release suspension for injection in pre-filled pen (BCise) (AstraZeneca UK Limited).

The following events listed below describe expected procedural/disease related AEs: The most frequent adverse reactions were mainly gastrointestinal related (nausea which was the most frequent reaction and associated with the initiation of treatment and decreased over time, and diarrhoea). In addition, injection site reactions (pruritus, nodules, erythema), hypoglycaemia (with a sulphonylurea), and headache occurred. Most adverse reactions associated with prolonged-release exenatide were mild to moderate in intensity.

9.3.4 *Seriousness*

All events are assessed for seriousness as defined for an SAE in section 9.1. Specific adverse events that require expedited reporting as SAEs are detailed in section 9.3.5.

9.3.5 *Other Notifiable Adverse Events*

Suspicion of chronic pancreatitis based on a rise in serum amylase greater than 50% above both baseline level AND the laboratory reference range will be notified in an expedited manner in the same way as an SAE.

Overdose and potential drug induced liver injury (DILI) events must be handled as SAEs (see section 9.8).

All safety events as described above will be treated as SAEs and reported in line with the procedures set-out in section 9.4 apart from regulatory reporting.

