## 7.8 Adverse event reporting

The number, nature and severity of serious adverse events (if any) will be reported separately by study arm at each follow up time point. The number of patients who experience adverse events will likewise be reported separately by study arm.

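### The SAE footnote excludes admission for any pre-existing condition, with no exception for worsening, so an unplanned admission for worsened MSA symptoms is not an SAE or SAR when hospitalisation is its only seriousness criterion

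*Protocol*

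**What the plan says.** The table in Protocol 9.1 defines serious adverse event, serious adverse reaction and unexpected serious adverse reaction in a single row. One of the criteria is that the event "requires hospitalisation or prolongation of existing hospitalisation". A footnote to that criterion has two sentences. The first is broad: "Hospitalisation is defined as an in-patient admission, regardless of length of stay". The second takes cases out: "Hospitalisation for pre-existing conditions, including elective procedures do not constitute an SAE".

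Protocol 9.3.4 refers every seriousness decision back to 9.1. Protocol 9.4 requires SAE forms to reach the sponsor within 24 hours of awareness. Protocol 9.5 sets 7-day and 15-day limits for SUSARs, which 9.1 defines as a kind of serious adverse reaction.

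On analysis, SAP 7.8 states: "The number, nature and severity of serious adverse events (if any) will be reported separately by study arm". For adverse events in general it promises only the number of patients affected, by arm.

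Safety of exenatide in MSA is a listed secondary outcome (Protocol 4; SAP 7.1.2), and preliminary safety data are part of the trial's stated purpose (Protocol 5.1).

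**The concern.** An exclusion of this kind usually serves to keep planned care for a stable condition out of the SAE count. This one goes further. Elective procedures are introduced by the word including, which makes them one example of what is excluded and not its limit. Nothing is said about worsening, or about worsening that the study drug may have caused.

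That matters here because every participant enters with a progressive disease. The background in Protocol 3 describes MSA as combining autonomic dysfunction, parkinsonism and cerebellar impairment. Protocol 3.1 lists constipation and dizziness as common risks of exenatide. COMPASS Select, completed at baseline (Protocol 8.1) and described in 8.6, covers "5 domains (orthostatic intolerance, secretomotor, bladder, constipation, and sleep". So the trial itself treats constipation and orthostatic intolerance as features a participant may already have. If such a feature worsens on exenatide and leads to admission, the footnote read literally calls this hospitalisation for a pre-existing condition.

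At stake is whether harm of that kind reaches the sponsor promptly and is described by arm in the report. The allocation is also known to everyone. Whether an admission is for the old condition or for a new event is a judgement, and in an open-label trial it could be made differently in the two arms.

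**Working it through.** No arithmetic decides this point. The check is to follow one case through the text: a participant with baseline constipation or orthostatic symptoms has an unplanned admission because they worsened, and no other seriousness criterion is met.

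1. **Is it an adverse event?** Yes. Protocol 9.1 says: "Therefore an AE can be any unfavourable or unintended change in the structure (signs), function (symptoms) or chemistry (laboratory data". Worsening of an existing symptom fits, and pre-existing disease is not excluded at this level.
2. **Is it hospitalisation?** Yes. Any in-patient admission counts.
3. **Is it serious by hospitalisation?** On the literal text, no. The condition was pre-existing, and neither document contains an exception for worsening, for unplanned admission or for a possible drug cause.
4. **Does drug-relatedness rescue it?** No. The same row defines serious adverse reactions, so an admission judged related is caught in the same way. If it is not a serious adverse reaction it cannot be a SUSAR, and the limits in 9.5 do not apply.
5. **Could another criterion make it serious?** Yes, if met. The footnote hangs on the hospitalisation criterion only. Death, threat to life, persistent or significant disability, and the important-medical-event clause carry no such exclusion.
6. **Does another section bring it back?** Protocol 9.3.5 adds a rise in amylase, overdose and possible drug-induced liver injury to the events handled as SAEs, but not worsening of MSA. Protocol 9.3.3 opens a list with "The following events listed below describe expected procedural/disease related AEs", yet the list names drug reactions only. That list concerns expectedness, so it would not settle seriousness in any case.
7. **What is kept?** Protocol 9.2 records all adverse events from consent to the week 58 call, and related ones after that. Protocol 9.3 has each assessed for severity, causality and seriousness; the fallback grading table in 9.3.1 places an indicated hospitalisation at Grade 3. The participant counts in the SAP 7.8 number of patients with adverse events.
8. **What is lost?** The 24-hour form (9.4), possible SUSAR status (9.5), a place among the SAEs that the Trial Management Group reviews (13.1), and the number, nature and severity listing by arm. The general count does not replace that listing. Protocol 3.1 lists nausea and diarrhoea as very common, so a participant admitted for worsened autonomic symptoms may already be in the count for another reason.

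**Size.** Neither document gives an admission rate or the share of admissions due to worsening of existing features, so the number affected cannot be derived. With about 25 patients per arm (Protocol 5.1), each patient whose only SAE is reclassified changes that arm's proportion with an SAE by 1/25 = 4 percentage points. This shows how sensitive the table is to a single decision, not how many such decisions there will be.

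**The case against.** The strongest reply is that the sentence is unclear rather than harmful. The mention of elective procedures suggests planned admissions were in mind. A symptom aggravated by exenatide is a new unfavourable change, and Protocol 9.3.2 calls it related whenever a relationship cannot be ruled out. An investigator could reasonably treat the admission as being for an adverse reaction. Protocol 3.1 also plays down the events in question, for example: "In most cases, constipation is transient and self limiting". MSA worsening is captured by arm through UMSARS, the ambulation, speech, swallowing and falls thresholds, and the use of drugs for orthostatic hypotension. The data monitoring committee advises on data and safety, not on SAEs alone. Finally, Protocol 9 places recording and reporting under the sponsor's SOP INV/S05, which may deal with worsening.

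Much of this stands as a limit on the point. The lenient reading is available, the SOP cannot be checked, and the overlap between dizziness and orthostatic intolerance is an inference. It does not remove the defect. The lenient reading is not written down, so two investigators could class the same admission differently. Efficacy scales do not record admissions or their cause. An SOP clause counting worsening as serious would conflict with the protocol definition, and the two would need reconciling.

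A reader might infer that all admissions for worsening MSA vanish from safety reporting. The documents do not support that: the events stay in the record as graded adverse events, and any that meet another seriousness criterion remain SAEs. A reader might also infer that most of the SAE table is lost or that an excess on exenatide will be hidden. Nothing in the documents gives a rate from which to conclude either.

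**Conclusion.** The footnote is wrong as written. Applied literally, it takes out of the SAE and SAR definitions any unplanned admission for worsening of a pre-existing condition, including worsening possibly caused by exenatide, when hospitalisation is the only seriousness criterion met. The loss is confined to expedited reporting, SUSAR eligibility and the by-arm description of nature and severity; recording and grading as an adverse event continue. Admissions for a distinct new event, such as an injury or infection, are not clearly covered and may still count. The number affected cannot be stated.

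The conclusion rests on the literal text and on the absence of any exception in the two documents. It assumes that SOP INV/S05 does not override the protocol definition. The possibility of different classification in the two arms follows from the open-label design and is a risk, not something shown. The point deserves correction because safety in MSA is a stated secondary outcome and the change is small.

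**What to change.** - **Protocol 9.1:** limit the exclusion to admissions that were planned before consent, or are elective, for a pre-existing condition that has not worsened since baseline. State that an unplanned admission for worsening of a pre-existing condition, MSA included, is assessed as an SAE, by the same rule in both arms.
- **SOP INV/S05:** check it against the new wording and reconcile any difference.
- **SAP 7.8:** show admissions judged to be MSA progression as a separate line by arm, so that they are visible without being mixed with other SAEs.

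The cost is a revised footnote, one table line and some additional SAE forms, many of them for disease progression. Under Protocol 9.5 those need no expedited report to the regulator or ethics committee unless they are judged both related and unexpected.
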